9.4.8 Treatment Compliance

Records of treatment compliance for each subject will be kept during the study. CRAs will review treatment compliance during visits and at the completion of the study.

9.4.9 Drug Supplies and Accountability

In compliance with local regulatory requirements, drug supplies will not be sent to the investigator until the following documentation has been received by the sponsor:

- A signed and dated confidentiality agreement
- Drug Enforcement Agency license
- A copy of the final protocol signature page, signed and dated by both the sponsor and investigator
- Written proof of approval of the protocol, the ICFs, and any other information provided to the subjects by the IRB for the institution where the study is to be conducted
- A copy of the IRB-approved ICF and any other documentation provided to the subjects to be used in this study
- The IRB membership list and statutes or Health and Human Services Assurance number
- A copy of the certification and a table of the normal laboratory ranges for the reference laboratory conducting the clinical laboratory tests required by this protocol
- An investigator-signed and dated Form FDA 1572
- Financial Disclosure form(s) for the principal investigator and all subinvestigators listed on Form FDA 1572
- A signed and dated curriculum vitae of the principal investigator including a copy of the principal investigator's current medical license or medical registration number on the curriculum vitae
- A signed and dated clinical site agreement

The investigator and the study staff will be responsible for the accountability of all treatment (dispensing, inventory, and record keeping) following the sponsor's instructions and adherence to GCP guidelines as well as local or regional requirements.

Under no circumstances will the investigator allow the treatment to be used other than as directed by this protocol. Parent/guardian may be dispensed treatment for pediatric subjects.

The site must maintain an accurate and timely record of the following: receipt of all study treatment, dispensing of treatment to the subject, collection and reconciliation of unused study treatment or reconciled study treatment to the sponsor or (where applicable) destruction of reconciled study treatment at the site. This includes, but may not be limited to: (a) documentation of receipt of study treatment, (b) treatment dispensing/return reconciliation

log, (c) treatment accountability log, (d) all shipping service receipts, (e) documentation of returns to the sponsor, and (f) certificates of destruction for any destruction of treatment that occurs at the site. All forms will be provided by the sponsor. Any comparable forms that the site wishes to use must be approved by the sponsor.

The treatment and inventory records must be made available, upon request, for inspection by a designated representative of the sponsor or a representative of a health authority. As applicable, all unused treatment and empty and partially empty containers from used study treatment are to be returned to the investigator by the subject and, together with unused study treatment that were shipped to the site but not dispensed to subjects, are to be returned to the sponsor's designated central or local depot(s) during the study or at the conclusion of the study, unless provision is made by the sponsor for destruction of treatment and containers at the site. Destruction at the site will only occur under circumstances where regulation or supply type prohibits the return of treatment to the central or local depot(s). Approval for destruction to occur at the site must be provided by the sponsor in advance. Upon completion of drug accountability and reconciliation procedures by the site's personnel and documentation procedures by the sponsor's personnel, treatment that are to be returned to the sponsor's designated central or local depot(s) must be boxed, sealed, and shipped back to the central or local depot(s) following all local regulatory requirements. In some regions, treatment may be removed from the site and hand delivered to the central or local depot by sponsor representatives. Where treatment is approved for destruction at the site, destruction will occur following the site's standard procedures and certificates of destruction will be provided to the sponsor.

Drug accountability will be reviewed during visits and at the completion of the study.

9.5 Study Assessments

9.5.1 Assessments

Assessments will be performed as specified in [Table 3](#).

9.5.1.1 Screening Assessments

9.5.1.1.1 DEMOGRAPHY

Subject demography information will be collected at the Screening Visit. Demography information includes date of birth, sex, race/ethnicity.

Height and weight will be measured at the Screening Visit.

9.5.1.1.2 MEDICAL HISTORY

Medical and surgical history and current medical conditions will be recorded at the Screening Visit. All medical and surgical history within 1 year must be noted in the Medical History and Current Medical Conditions case report form (CRF).

9.5.1.1.3 EPILEPSY HISTORY

Epilepsy history will be recorded at Screening Visit as designated in the Schedule of Procedures/Assessments ([Table 3](#)). Epilepsy history will include information on genetic mutation related to epilepsy, if available.

9.5.1.2 Efficacy Assessments

9.5.1.2.1 SEIZURE COUNTS

Seizure diaries will be used to collect seizure counts. Diaries will be dispensed to all subjects at each visit as described in [Table 3](#). The diary is to be completed daily, by the parent/guardian. All seizures will be recorded. At each visit the parent/guardian will be instructed by the site personnel as to how to complete the diary and reminded that they must return the diary at their next scheduled clinic visit and at the Early Discontinuation and Follow-up Visits (if applicable). To ensure correct seizure classification, the medically qualified investigator should review the diary with the parent/guardian at all visits. Parents/guardians must be counseled if diary compliance is not satisfactory (ie, missed 3 or more consecutive daily diary entries).

9.5.1.2.2 CLINICAL GLOBAL IMPRESSION

CGIC (clinician-rated) will be assessed. CGIC is a 7-point scale that provides a clinician-determined summary measure of change from baseline of subject's clinical status.

9.5.1.3 Pharmacokinetic, Pharmacodynamic, Pharmacogenomic, and Other Biomarker Assessments

9.5.1.3.1 PHARMACOKINETIC ASSESSMENTS

Blood samples for PK assessment will be collected during the Treatment Period.

Blood samples with sodium heparin as anticoagulant (1 mL each) will be collected as specified in [Table 3](#). See PK or laboratory manual for a description of collection, handling, and shipping procedures for PK samples.

Samples from all subjects receiving active treatment will be analyzed. In addition, a predetermined percentage of placebo samples will be analyzed. Remaining placebo samples will be held in storage in the event that further confirmatory analysis is requested. Plasma concentrations of lorcaserin will be quantified by liquid chromatography with tandem mass spectrometry methodology using a previously validated assay.

Blood will also be drawn where possible at the first report of a serious adverse event (SAE) or severe unexpected AE and at its resolution.

9.5.1.3.2 PHARMACODYNAMIC, PHARMACOGENOMIC, AND OTHER BIOMARKER, ASSESSMENTS

Data may be analyzed based on types of genetic mutations related to epilepsy (information on genetic mutation related to epilepsy will be collected, if available, based on review of epilepsy history).

9.5.1.4 Safety Assessments

Safety assessments will consist of monitoring and recording all AEs, regular laboratory evaluation for hematology, blood chemistry, and urinalysis; periodic measurement of vital signs, weight, echocardiograms, and ECGs; and the performance of physical and neurological examinations, as detailed in [Table 3](#).

An assessment of suicidality using the C-SSRS (for subjects aged ≥ 6 years old) or based upon clinical assessment of the investigator (for subjects < 6 years old) will be performed at every study visit. The C-SSRS provides assessment of suicide risk including the severity and immediacy of that risk through a series of plain-language questions.

Valvular regurgitation as assessed on echocardiogram will be rated absent, trace, mild, moderate, or severe for the aortic, mitral, tricuspid, and pulmonic valve. The evaluations will be based on the recommendations from the American Society of Echocardiography ([Zoghbi et al., 2017](#)). Pulmonary artery pressure will be estimated by a comprehensive approach that includes the tricuspid regurgitation jet velocity (if present), right ventricular outflow tract flow acceleration time, pulmonic regurgitation peak early diastolic velocity (if present), right ventricular outflow tract flow acceleration time, pulmonic regurgitation peak early diastolic velocity (if present), and the eccentricity index that describes the interventricular septum position at end-systole ([Jone and Ivy, 2014](#)).

9.5.1.4.1 ADVERSE EVENTS

An AE is any untoward medical occurrence in a patient or clinical investigation subject administered an investigational product. An AE does not necessarily have a causal relationship with the medicinal product. For this study, the study drug is E2023 or placebo.

The criteria for identifying AEs in this study are:

- Any unfavorable and unintended sign (including an abnormal laboratory finding), symptom, or disease temporally associated with the use of an investigational product, whether or not considered related to the investigational product (Note: Every sign or symptom should not be listed as a separate AE if the applicable disease [diagnosis] is being reported as an AE)
- Any new disease or exacerbation of an existing disease. However, worsening of the primary disease should be captured under efficacy assessments as disease progression.
- Any deterioration in nonprotocol-required measurements of a laboratory value or other clinical test (eg, ECG or x-ray) that results in symptoms, a change in treatment, or discontinuation of study drug

- Recurrence of an intermittent medical condition (eg, headache) not present pretreatment (Baseline)
- An abnormal laboratory test result should be considered an AE if the identified laboratory abnormality leads to any type of intervention, withdrawal of study drug, or withholding of study drug, whether prescribed in the protocol or not.

All AEs, regardless of relationship to study drug or procedure, should be recorded beginning from the time the subject signs the study ICF through the last visit of the End of Treatment Phase. Refer to [Section 9.5.4.1](#) for the time period after the end of treatment for SAE collection.

Abnormal laboratory values should not be listed as separate AEs if they are considered to be part of the clinical syndrome that is being reported as an AE. It is the responsibility of the investigator to review all laboratory findings in all subjects and determine if they constitute an AE. Medical and scientific judgment should be exercised in deciding whether an isolated laboratory abnormality should be classified as an AE. Any laboratory abnormality considered to constitute an AE should be reported on the Adverse Event CRF.

Abnormal ECG (QTc using Fridericia's formula) results, if not otherwise considered part of a clinical symptom that is being reported as an AE, should be considered an AE if the QTc using Fridericia's formula is more than 460 ms and there is an increase of more than 60 ms from baseline. If subject has a normal ECG baseline reading, but during any visit thereafter the QT is measured as more than 460 ms, 3 consecutive ECGs separated by 5 to 10 minutes will be performed to confirm the abnormality. Any ECG abnormality that the investigator considers as an AE should be reported as such.

It is the responsibility of the investigator to review the results of the clinical assessment of suicidality, C-SSRS, in all subjects and determine if any result constitutes an AE. Medical and scientific judgment should be exercised in deciding whether an isolated suicidality rating scale response should be classified as an AE.

All AEs must be followed for 28 days after the subject's last dose, or until resolution, whichever comes first. All SAEs must be followed to resolution or, if resolution is unlikely, to stabilization.

Every effort must be made by the investigator to categorize each AE according to its severity and its relationship to the study treatment.

Assessing Severity of Adverse Events

AEs will be graded on a 3-point scale (mild, moderate, severe) and reported in the detail indicated on the CRF. The definitions are as follows:

Mild Discomfort noticed, but no disruption of normal daily activity

Moderate Discomfort sufficient to reduce or affect normal daily activity

Severe Incapacitating, with inability to work or to perform normal daily activity

The criteria for assessing severity are different than those used for seriousness (see [Section 9.5.1.4.2](#) for the definition of an SAE).

Assessing Relationship to Study Treatment

Items to be considered when assessing the relationship of an AE to the study treatment are:

- Temporal relationship of the onset of the event to the initiation of the study treatment
- The course of the event, especially the effect of discontinuation of study treatment or reintroduction of study treatment, as applicable
- Whether the event is known to be associated with the study treatment or with other similar treatments
- The presence of risk factors in the study subject known to increase the occurrence of the event
- The presence of nonstudy, treatment-related factors that are known to be associated with the occurrence of the event

Classification of Causality

The relationship of each AE to the study drug will be recorded on the CRF in response to the following question:

Is there a reasonable possibility that the study drug caused the AE?

Yes (related) A causal relationship between the study drug and the AE is a reasonable possibility

No (not related) A causal relationship between the study drug and the AE is not a reasonable possibility

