9.5.1.4.8 ELECTROCARDIOGRAMS

ECGs will be obtained as designated in the Schedule of Procedures/Assessments ([Table 3](#)). If subject has a normal ECG baseline reading, but during any visit thereafter the QT is measured as more than 460 ms, 3 consecutive ECGs separated by 5 to 10 minutes will be performed to confirm the abnormality.

An ECG abnormality may meet the criteria of an AE as described in this protocol (see [Section 9.5.1.4.1](#)) and the CRF Completion Guidelines. In these instances, the AE corresponding to the ECG abnormality will be recorded on the Adverse Events CRF.

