Week	From -4 Weeks to Week 0	0	1	2	4	6	10	14	4 weeks after the last dose		
Procedures/Assessments											

PedsQL = Pediatric Quality of Life Inventory, PK = pharmacokinetic, QoL = Quality of Life in Epilepsy Scale/Pediatric Quality of Life Inventory 4.0; QOLIE-31 = Quality of Life in Epilepsy Survey.

- a: All visits to be done within ± 3 days of the schedule. If any of the visits after Visit 1 are conducted remotely due to the COVID-19 pandemic, at a minimum, the following assessments should be conducted: AEs, suicidality assessment, concomitant medications, review of seizure diary data, and study drug compliance (any missed or extra doses with dates). Study drug and seizure diary may be picked up from the site by the subject/caregiver or shipped from the site to the subject's location. C-SSRS and Clinical Global Impression may be conducted remotely over the phone by a qualified rater and QOLIE-31 and PedsQL based on input from subject over the phone.
- b: Visit to be done within ± 7 days of the schedule.
- c: The Follow-up Visit only applies to those subjects who do not enter the Extension Phase after completion of this study.
- d: These assessments will be conducted for subjects who discontinue the study or treatment early for any reason after Visit 2.
- e: At Unscheduled Visits these assessments/procedures conducted if needed.
- f: Epilepsy history will include information on genetic mutation related to epilepsy, if available.
- g: Unused study drug to be retrieved and study drug dispensed only for subjects requiring dose change at Unscheduled Visits.
- h: Study drug and seizure diary will be dispensed only for subjects who enter the Extension Phase.
- i: Physical and neurological examinations will only be performed at the indicated visits. For all other clinic visits during the study, the physical and the neurological examinations will only be performed when there is a complaint from the subject. Clinically significant abnormal findings from the physical or the neurological examinations will be reported as AEs.
- j: Clinical laboratory tests include hematology, blood chemistry, and urinalysis.
- k: At Unscheduled Visits, these assessments will only be done if the results from the previous visit were deemed clinically significant by the investigator.
- l: Only for female subjects of child-bearing potential (defined as all postmenarche females, unless postmenopausal or have been sterilized surgically).

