- m: If subject has a normal ECG baseline reading, but during any visit thereafter the QT is measured as >460 ms, 3 consecutive ECGs separated by 5 to 10 minutes will be performed to confirm the abnormality.
- n: One blood sample (approximately 1 mL) for determination of lorcaserin plasma concentrations will be collected at predose and between 1 to 2 hours postdose at Visit 4 and 6; 3 to 6 hours postdose only at Visit 5 and 7.

Table 3 Schedule of Procedures/Assessments in Study E2023-A001-304: Core Study

Phase	Prerandomization	Randomization									
Period	Screening/Baseline	Treatment ^a							Follow-up ^{b,c}		
Visit	1	2	3	4	5	6	7	8		ED ^d	Unscheduled ^e
Week	From -4 Weeks to Week 0	0	1	2	4	6	10	14	4 weeks after the last dose		
Procedures/Assessments											

o: At ED Visit, 1 blood sample (approximately 1 mL) PK samples should only be collected only if can be drawn within 50 hours of the last dose of study drug.

p: Clinical Global Impression of Severity is conducted At Visit 2, and Clinical Global Impression of Change at Visit 8 or ED.

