- d: These assessments will be conducted for subjects who discontinue the study or treatment early for any reason after Visit 9.
- e: At Unscheduled Visits these assessments/procedures conducted if needed.
- f: Unused study drug to be retrieved and study drug dispensed only for subjects requiring dose change at Unscheduled Visits.
- g: Physical and neurological examinations will only be performed at the indicated visits. For all other clinic visits during the study, the physical and the neurological examinations will only be performed when there is a complaint from the subject. Clinically significant abnormal findings from the physical or the neurological examinations will be reported as AEs.
- h: Clinical laboratory tests include hematology, blood chemistry, and urinalysis.
- i: At Unscheduled Visits, these assessments will only be done if the results from the previous visit were deemed clinically significant by the investigator.
- j: Only for female subjects of child-bearing potential (defined as all postmenarche females, unless postmenopausal or have been sterilized surgically).
- k: If subject has a normal ECG baseline reading, but during any visit thereafter the QT is measured as >460 ms, 3 consecutive ECGs separated by 5 to 10 minutes will be performed to confirm the abnormality.

Table 4 Schedule of Procedures/Assessments in Study E2023-A001-304: Extension Phase

Phase	Extension							
Period	Treatment ^a					Follow-up ^{b,c}		
Visit	9	10	11	12	13		ED ^d	Unscheduled ^e
Week	15	17	20	23	26	4 weeks after the last dose		
Procedures/Assessments								

l: Clinical Global Impression of Change at Visit 13 or ED.

m: One blood sample (approximately 1 mL) for determination of lorcaserin plasma concentration will be collected at predose and between 1 to 2 hours postdose at Visit 9, 11, and 13; 3 to 6 hours postdose only at Visit 10 and 12.

n: At ED, 1 blood sample (approximately 1 mL) PK samples should be collected only if samples can be drawn within 50 hours of the last dose of study drug.

Statistical Methods

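### The mandatory repeat-ECG trigger is written on uncorrected QT above 460 ms in all four places, so at heart rates above 60 bpm a band of prolonged QTcF values need not be confirmed at the same visit

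*Protocol*

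**What the plan says.** Protocol 9.5.1.4.1 has two ECG rules in consecutive sentences.

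- **AE rule.** An abnormal ECG not already part of a reported clinical event counts as an AE if the QTc by Fridericia's "formula is more than 460 ms and there is an increase of more than 60 ms from baseline". Both limbs are needed.
- **Repeat rule.** If the baseline ECG was normal and "during any visit thereafter the QT is measured as more than 460 ms, 3 consecutive ECGs separated by 5 to 10 minutes" must be done. Their stated purpose follows: "to confirm the abnormality. Any ECG abnormality that the investigator considers as an AE should be reported as such".

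The repeat rule recurs three times, each time on QT with no correction named:

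- 9.5.1.4.8: "during any visit thereafter the QT is measured as more than 460 ms"
- Table 3 footnote m (Core Study): "the QT is measured as >460 ms, 3 consecutive ECGs separated by 5 to 10 minutes"
- Table 4 footnote k (Extension Phase): "during any visit thereafter the QT is measured as >460 ms, 3 consecutive ECGs"

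Exclusion criterion 11 (9.3.2) gives a repeatedly shown QTc above 460 ms as its example of marked prolongation. The protocol's abbreviation list defines QTc as the corrected interval. The SAP plans ECG summaries (5.6.5) and does not restate or clarify the trigger.

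**The concern.** The cutoff is 460 ms in both rules, but one applies it to QTcF and the other, as worded, to raw QT. The two measures agree only at 60 bpm. At faster rates QTcF exceeds QT, so an ECG can be prolonged by the protocol's own QTcF standard without reaching the written repeat threshold. The study admits children from age 2. Resting rates above 60 bpm in such children are an assumption, since the documents give no heart rates, but not a strained one.

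At stake is the confirmation step. Scheduled ECGs are sparse: screening, Visit 8 (Week 14) and Visit 13 (Week 26), plus early discontinuation. A prolonged QTcF at Visit 8 could therefore rest on one tracing, with the next scheduled ECG 12 weeks later.

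**Working it through.** **Inputs.** The trigger is QT above 460 ms (four places listed above). The AE rule is QTcF above 460 ms with a rise above 60 ms (9.5.1.4.1). The number randomized is 22 (SAP 7). Heart rates (HR) are an assumed range. The plan states no figure to reproduce here.

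**Formula.** QTcF = QT / RR^(1/3), with RR = 60/HR in seconds and HR in bpm.

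**Step 1: QTcF at which the literal trigger starts to fire.** Put QT = 460 ms: QTcF = 460 / (60/HR)^(1/3).

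| HR (bpm) | QTcF when raw QT is 460 ms | QTcF values above 460 ms not repeated |
|---|---|---|
| 50 | 432.9 | none (mismatch reverses) |
| 60 | 460.0 | none (limits coincide) |
| 70 | 484.3 | 460 to 484 |
| 80 | 506.3 | 460 to 506 |
| 100 | 545.4 | 460 to 545 |
| 120 | 579.6 | 460 to 580 |

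**Step 2: heart rate from which a given QTcF escapes.** Raw QT is at or below 460 ms when HR ≥ 60 × (QTcF/460)^3.

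- QTcF 470 ms: 64.0 bpm
- QTcF 480 ms: 68.2 bpm
- QTcF 500 ms: 77.1 bpm
- QTcF 520 ms: 86.7 bpm

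**Step 3: can such an ECG also meet the AE rule?** Yes, if baseline QTcF was low enough. Take assumed values of 410 ms at baseline and 480 ms on treatment at 100 bpm. The rise is 480 − 410 = 70 ms, so both limbs of the AE rule are met. Raw QT is 480 × 0.6^(1/3) = 404.8 ms, so no repeat is required. At QTcF 480 ms, a baseline below 480 − 60 = 420 ms is needed.

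**Step 4: the reverse case.** At 50 bpm a raw QT of 470 ms gives QTcF = 470 / 1.2^(1/3) = 442.3 ms. The literal trigger fires although QTcF is below 460 ms. The cost is only extra ECGs, and exclusion criterion 12 bars a history of clinically significant bradycardia.

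**Step 5: exposure.** Each subject has at most two scheduled on-treatment ECGs (Visits 8 and 13), so the ceiling is 22 × 2 = 44 if all complete both phases, plus early-discontinuation or unscheduled ECGs.

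**Step 6: effect of the fix.** With the trigger on QTcF above 460 ms, it matches the first limb of the AE rule at every heart rate. The raw QT above which repeats are required becomes 417.9 ms at 80 bpm, 388.0 at 100 and 365.1 at 120.

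**The case against.** The strongest reply is that a corrected interval was plainly meant. The paragraph in 9.5.1.4.1 opens on QTcF, the trigger follows with the same number, and the repeats are to confirm an abnormality just defined in QTcF terms. Exclusion criterion 11 pairs the same 460 ms with the same idea of repeated demonstration, in QTc. Section 9.5.1.4.8 refers back to 9.5.1.4.1 and to case report form (CRF) completion guidelines, which may name the parameter and are not available here. On this view the text is loose shorthand. It is also fair that the two rules serve different purposes, so no subject receives contradictory instructions.

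Most of this stands: the intended reading probably is QTcF. It does not remove the point. The protocol defines QTc separately from QT, no sentence equates them, and the two table footnotes stand alone without the QTcF context. A site working from the schedule sees only QT.

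Two stronger readings are tempting and are not supported.

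- A reader might infer that every ECG meeting the AE rule above 60 bpm escapes repetition. It does not: at 100 bpm a QTcF above about 545 ms has raw QT above 460 ms and must be repeated. The gap is also confined to subjects with a normal baseline ECG, because the trigger applies only to them.
- A reader might infer that QTcF events go undetected or unreported. The AE rule runs on QTcF without needing repeats, the investigator reports any ECG abnormality judged an AE, and "All AEs must be followed for 28 days after" the last dose or until resolution, whichever comes first. Unscheduled ECGs are also available, although "these assessments will only be done if the results from the previous visit were deemed clinically significant by the investigator".

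**Conclusion.** The point holds as a minor mis-specification of a safety procedure. Read literally, in a subject with a normal baseline ECG and a heart rate above 60 bpm, a QTcF above 460 ms with raw QT at or below 460 ms need not be confirmed at that visit, whether or not the AE rule is also met. The size of the gap depends on heart rate as tabulated. How often it occurs cannot be derived, because the documents give no heart rates or QTc data.

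The loss is limited to required same-visit confirmation. No dose, stopping or analysis rule uses the confirmed value, and no efficacy or sample-size figure changes. The conclusion rests on sites following the literal wording. If they, or the CRF guidelines, already read QT as QTcF, nothing was lost in practice and the change is a clarification.

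**What to change.** Replace the words 'the QT' with 'the QTcF (Fridericia)' in the four trigger statements (9.5.1.4.1, 9.5.1.4.8, Table 3 footnote m, Table 4 footnote k) and keep 460 ms. Exclusion criterion 11 needs no change. The cost is wording in four places and a few more repeat ECGs at heart rates above 60 bpm; QTcF is already needed for the AE rule.

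SAP 7 records that the sponsor has decided to terminate the study, so the rewording may have little practical effect. An optional step at reporting is one listing of on-treatment ECGs with QTcF above 460 ms and raw QT at or below 460 ms that were not repeated, in subjects with a normal baseline ECG, if those fields were captured. It would show which prolonged values rest on a single tracing, which the planned by-visit summaries would not. It adds little, because it flags ECGs that the written rule did not require to be repeated, and the fix does not depend on it.
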